- At least half of the patients (minimum of 2 patients) achieve the target exposure leading to continuous inhibition of extracellular arginase 1 by > 90% (a trough [Cmin] plasma concentration of INCB001158 at steady state of  $\geq 1$   $\mu$ M), AND/OR
- At least half of the patients (minimum of 2 patients) achieve a 2.5-fold increase in fasting plasma arginine at Cycle 1 Day 15 predose relative to their baseline (Cycle 1 Day 1 predose) value.

Population PK modeling showed a highly predictable, linear, inverse relationship between CrCl and AUC, Cmax, and half-life for INCB001158 (see Section 10.2.2.1). Therefore, if the PK-PD criteria specified above are not met at the 50 mg BID dose, population PK modeling will be used to determine whether a lower dose (25 mg BID) or a previously evaluated intermediate dose (75 mg BID) would more closely approximate PK parameters for the established RP2D of 100 mg BID. Cohort 1c patients who do not complete all planned PK assessments or have treatment discontinuation or interruptions during the first 21 days of dosing will be replaced until 6 evaluable patients have been accrued to the cohort. Patients meeting the pre-specified PK and PD criteria will be counted towards the Simon 2-stage efficacy assessment in their respective Part 3 expansion cohorts, provided these have not fully enrolled at the time data from these patients become available.

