**Table 12.1-1: INCB001158 Dose Modification Guidelines for Adverse Events in Patients Receiving INCB001158 (All Parts)**

Adverse Reaction	Severity	Management	Study Drug Dose Modification
Evidence of urea cycle inhibition	
 
Fasting urinary orotic acid > 2 X and <math>\leq</math> 10 X ULN
 
Any urinary orotic acid > 2 X and <math>\leq</math> 40 X ULN
 
	
 
Re-test fasting urinary orotic acid 1 week later.
 
	
 
None.
 

	
 
Ammonia 2 X ULN and 2 X baseline (repeated measurements or with symptoms)
 
Fasting urinary orotic acid > 10 X ULN
 
Any urinary orotic acid > 40 X ULN
 
BUN < 50% LLN
 
	
 
See Section 12.1.3.3 for management of hyperammonemia.
 
	
 
Interrupt study drug.
 
Consider restarting (at a lower dose) in consultation with Medical Monitor.
 

Study drug-related creatinine increase  (patients with CrCl 30-49 mL/min at baseline)	Grade 2 (> 1.5-3.0 X baseline)	Weekly testing of serum creatinine during interruption of study drug.	
 
Interrupt study drug.
 
1st event: Restart at same dose upon resolution to <math>\leq</math> Grade 1.
 
2nd event: Restart at 25 mg BID upon resolution to <math>\leq</math> Grade 1.
 

	Grade 3 (> 3.0 baseline) or 4 (dialysis indicated)	Weekly testing of serum creatinine during interruption of study drug.	
 
Interrupt study drug and do weekly serum creatinine testing and urinalysis until serum creatinine returns to <math>\leq</math> Grade 1. Restart study drug at 25 mg BID.
 
If after 4 weeks the serum creatinine has not recovered to <math>\leq</math> Grade 1, permanently discontinue study drug.
 
If after restarting study drug the toxicity reoccurs, permanently discontinue study drug.
 

**Table 12.1-1: INCB001158 Dose Modification Guidelines for Adverse Events in Patients Receiving INCB001158 (All Parts) (Continued)**

Adverse Reaction	Severity	Management	Study Drug Dose Modification

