Study drug-related creatinine increase  (patients with CrCl > 50 mL/min at baseline)	Grade 2 (> 1.5-3.0 X baseline OR > 1.5-3.0 X ULN)	Weekly testing of serum creatinine during interruption of study drug.	
 
Interrupt study drug.
 
1st event: Restart at same dose upon resolution to ≤ Grade 1.
 
2nd event: Restart at 25 mg BID upon resolution to ≤ Grade 1.
 

	Grade 3 (> 3.0 baseline; > 3.0-6.0 X ULN) or 4 (> 6.0 X ULN)	Weekly testing of serum creatinine during interruption of study drug.	
 
Interrupt study drug and do weekly serum creatinine testing and urinalysis until serum creatinine returns to ≤ Grade 1. Restart study drug at 25 mg BID.
 
If after 4 weeks the serum creatinine has not recovered to ≤ Grade 1, permanently discontinue study drug.
 
If after restarting study drug the toxicity reoccurs, permanently discontinue study drug.
 

Suspected immune-related adverse event (irAE) including: 
 
Colitis
 
Pneumonitis
 
Dermatitis
 
Hepatitis
 
Hypophysitis
 
Adrenal insufficiency
 
Type I diabetes mellitus
 
Nephritis
 
	Grade 1	
 
Symptomatic therapy, as appropriate
 
	No change
	Grade 2	
 
If > 5 days, 0.5 to 1 mg/kg/day prednisone. If worsening or no improvement, increase to 1 to 2 mg/kg/day prednisone equiv. and consider IV.
 
	
 
Interrupt study drug.
 
1st event: Restart at same dose upon resolution to ≤ Grade 1.
 
2nd event: Restart one dose level lower for second event of the same AE.
 

	Grade 3	
 
1 to 2 mg/kg/day prednisone equiv. Consider IV.
 
	
 
Interrupt study drug.
 
1st event: Consider restarting at next lower dose level upon resolution to ≤ Grade 1.
 
2nd event: Permanently discontinue.
 

	Grade 4	
 
1 to 2 mg/kg/day prednisone equiv. Consider IV.
 
	
 
Permanently discontinue.
 

**Table 12.1-1: INCB001158 Dose Modification Guidelines for Adverse Events in Patients Receiving INCB001158 (All Parts) (Continued)**

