Adverse Reaction	Severity	Management	Study Drug Dose Modification
All others	Grade 1	Symptomatic therapy, as appropriate.	No change.
	Grade 2	Symptomatic therapy, as appropriate.	
 
Interrupt study drug.
 
1st event: Restart at same dose upon resolution to <math>\leq</math> Grade 1.
 
2nd event: Restart one dose level lower for second event of the same AE.
 

	Grade 3	Symptomatic therapy, as appropriate.	
 
Interrupt study drug.
 
1st event: Consider restarting at next lower dose level upon resolution to <math>\leq</math> Grade 1.
 
2nd event: Permanently discontinue.
 

	Grade 4	Symptomatic therapy, as appropriate.	
 
Permanently discontinue.
 

 For creatinine increases that are unrelated to study drug (e.g. obstructive uropathy) INCB001158 may be continued at a dose appropriate for the new CrCl (as calculated by the Cockcroft-Gault formula) as follows:

- CrCl > 50 mL/min: Continue INCB001158 at 100 mg BID.
- CrCl 30-49 mL/min: Reduce INCB001158 to 50 mg BID.
- CrCl < 30 mL/min: Hold INCB001158 and restart once CrCl > 30 mL/min as specified above.

**Table 12.1-2: Dose Modification and Toxicity Management Guidelines for Immune-Related Adverse Events Associated With Pembrolizumab (Parts 1b, 1c, and 3)**

General instructions				
1. Severe and life-threatening irAEs should be treated with IV corticosteroids followed by oral steroids. Other immunosuppressive treatment should begin if the irAEs are not controlled by corticosteroids. 2. Pembrolizumab must be permanently discontinued if the irAE does not resolve or the corticosteroid dose is not $\leq 10$ mg/day within 12 weeks of the last pembrolizumab treatment. 3. The corticosteroid taper should begin when the irAE is $\leq$ Grade 1 and continue at least 4 weeks. 4. If pembrolizumab has been withheld, pembrolizumab may resume after the irAE decreased to $\leq$ Grade 1 after corticosteroid taper.				
irAEs	Toxicity Grade (CTCAE V4.0)	Action With Pembrolizumab	Corticosteroid and/or Other Therapies	Monitoring and Follow-up

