**Any SAE occurring during pregnancy must be recorded on the SAE report form and submitted to the sponsor or designee.**

#### **16.5 Definition of an Overdose for This Protocol and Reporting of Overdose to the Sponsor**

For this study, an overdose of each study treatment is defined as follows:

- INCB001158: A dose that is higher than the dose that patient has been intended to receive, which could be either the originally assigned dose (if not subsequently modified) or a modified dose (eg, following a dose reduction).
- Pembrolizumab: A dose  $\geq$  1000 mg (5 times the dose).

No specific information is available on the treatment of overdose of INCB001158 or pembrolizumab. In the event of overdose, the patient should be observed closely for signs of toxicity. Appropriate supportive treatment should be provided if clinically indicated.

If an AE(s) is associated with ("results from") the overdose of study treatments, then the AE(s) is reported as an SAE, even if no other seriousness criteria are met.

All reports of overdose must be reported within 24 hours to the sponsor either by electronic media or paper.

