5.2. Treatment Groups

In Part 1a, participants with advanced or metastatic solid tumors will be enrolled in INCB001158 monotherapy treatment groups for dose escalation. In Part 2, participants with specific tumor types will be enrolled to receive INCB001158 monotherapy at the RP2D.

In Parts 1b and 1c, participants with advanced or metastatic solid tumors specified in the expansion cohorts will be enrolled in INCB001158 + pembrolizumab combination treatment groups for dose escalation (Part 1b) and safety assessments for participants with renal impairment (Part 1c). In Part 3, participants with specific tumor types will be enrolled to receive INCB001158 at the RP2D + pembrolizumab. Treatment groups and INCB001158 and pembrolizumab dose levels are outlined in Table 2.

Part	Treatment Group	Drug	Dose
Part 1a	INCB001158 monotherapy	INCB001158	50-150 mg PO BID
Part 1b	INCB001158 + pembrolizumab	INCB001158	50-100 mg PO BID
		Pembrolizumab	200 mg IV on Day 1 of each 21-day cycle
Part 1c	INCB001158 + pembrolizumab ^a	INCB001158	50 mg PO BID
		Pembrolizumab	200 mg IV on Day 1 of each 21-day cycle
Part 2	INCB001158 monotherapy	INCB001158	RP2D from Part 1a
Part 3	INCB001158 + pembrolizumab	INCB001158	RP2D from Part 1b
		Pembrolizumab	200 mg IV on Day 1 of each 21-day cycle

 Table 2:
 Treatment Groups for Participants Enrolled

^a Participants with impaired renal function.

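### Footnote 1 of Table 12.1-1 lists fixed doses by creatinine clearance alone and so contradicts the lower assigned and reduced doses set elsewhere in the protocol

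*Protocol*

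**What the plan says.** The title of Protocol Table 12.1-1 gives its scope: "INCB001158 Dose Modification Guidelines for Adverse Events in Patients Receiving INCB001158 (All Parts").

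Footnote 1 of that table deals with creatinine increases unrelated to study drug, such as those from urinary obstruction. It opens: "INCB001158 may be continued at a dose appropriate for the new CrCl (as calculated by the Cockcroft-Gault formula) as follows". Three lines follow:

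- "CrCl > 50 mL/min: Continue INCB001158 at 100 mg BID"
- "CrCl 30-49 mL/min: Reduce INCB001158 to 50 mg BID"
- For CrCl below 30 mL/min, hold the drug, and restart it by the lines above once CrCl exceeds 30.

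Elsewhere the documents place patients on other doses:

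- **Assigned doses.** SAP Table 2 (Section 5.2) gives "50-150 mg PO BID" for Part 1a and 50 to 100 mg BID for Part 1b. Protocol Section 10.2.2.1 names the levels: 50, 75, 100 and 150 mg BID as monotherapy, and 50, 75 and 100 mg BID with pembrolizumab.
- **Drug-related creatinine increases.** In the same Table 12.1-1, a second Grade 2 event, or a Grade 3 or 4 event, leads to a restart at 25 mg BID. This applies to both baseline CrCl groups.
- **Other adverse events.** The rows for immune-related and other events say, for Grade 2, "Restart one dose level lower for second event of the same AE". In Table 5.1-1, one level below 100 mg BID is 75 mg BID.

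For CrCl 30-49, Section 5.1 (Part 1c) starts at 50 mg BID. If the PK and pharmacodynamic criteria are not met there, "population PK modeling will be used to determine whether a lower dose (25 mg BID") or 75 mg BID would come closer to the exposure at the recommended Phase 2 dose (RP2D).

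**The concern.** The footnote names absolute doses and uses one input, the new CrCl. It does not refer to the assigned dose, the dose in force or any earlier reduction for toxicity. Nothing in the table limits it to patients taking 100 mg BID, and the title extends it to everyone.

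For a patient on less than the listed dose, two instructions in one table therefore disagree: one has lowered the dose for toxicity, and the other lists a higher one. The disagreement would arise when renal function has just worsened, and Section 10.2.2.1 describes renal clearance as the presumed main route of elimination. What is at stake is that a reduction made for toxicity could be undone by someone following the table.

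**Working it through.** **1. Apply the footnote literally to each dose a patient could be on.** Ratio = listed dose / current dose.

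| Current dose (mg BID) | How the patient got there | New CrCl | Listed dose (mg BID) | Ratio |
|---|---|---|---|---|
| 25 | Reduced for a drug-related creatinine event | 30-49, or restart in that band after a hold | 50 | 50/25 = 2.00 |
| 25 | Same | above 50 | 100 | 100/25 = 4.00 |
| 50 | Assigned in Part 1a or 1b | above 50 | 100 | 100/50 = 2.00 |
| 75 | Assigned, or one level below 100 | above 50 | 100 | 100/75 = 1.33 |
| 100 | RP2D | above 50 | 100 | 1.00 |
| 100 | RP2D | 30-49 | 50 | 0.50 |

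The verbs *Continue* and *Reduce* fit only the last two rows. In the other four the listed dose exceeds the current one.

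**2. The restart line is the clearest case.** In the first two bands, a site might notice that *Continue* or *Reduce* does not fit a patient already on less. After a hold there is no such cue. The patient is off drug, and the site looks up a restart dose. A patient previously cut to 25 mg BID, held for CrCl below 30 and recovering to CrCl 40, is listed at 50 mg BID.

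**3. Size in exposure.** Table 10.2-1 gives projected steady-state AUC without a unit, so only ratios are used. Its columns are dose-proportional. At CrCl 50, 2 × 13,413 = 26,826 (the 100 mg entry) and 1.5 × 13,413 = 20,119.5 (75 mg entry 20,120). The dose ratio therefore carries straight over to AUC at a given CrCl:

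- 50 to 100 mg at CrCl 60: 22,855 / 11,428 = 2.00
- 75 to 100 mg at CrCl 60: 22,855 / 17,141 = 1.33
- 25 to 50 mg at CrCl 40: the table has no 25 mg column. By proportionality 25 mg gives 16,391 / 2 ≈ 8,196, and 16,391 / 8,196 = 2.00

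**4. Check the bands against eligibility.** Table 7.1-1 admits CrCl of 50 or more (all parts except 1c) and 30-49 (Part 1c). The footnote bands are above 50, 30-49 and below 30. A patient at exactly 50 is eligible but falls in no band, and a calculated value between 49 and 50 also falls in none. A held patient who recovers to exactly 30 is inside the 30-49 band but does not meet the restart condition of more than 30.

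**5. Compare the 30-49 line with Part 1c.** Section 5.1 leaves open a move from 50 mg BID to 25 or 75 mg BID. The footnote states 50 mg BID with no cross-reference to that result.

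**The case against.** The strongest reply is that the footnote was plainly written with a patient on 100 mg BID in mind. *Continue* at 100 and *Reduce* to 50 make sense only for that patient. The opening is permissive. Section 12.1.3.1 says the table is guidance that does not override the treating physician's judgment, and it asks investigators to contact the Medical Monitor when a dose modification is planned. All of this stands and makes a wrong dose less likely. It does not supply the missing limit on scope, and the restart line lacks the verbal cue.

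It can also be said that 50 mg BID is the model-based working dose for CrCl 30-49, so using it before Part 1c reports is a matter of sequence and not a conflict. That is fair. What remains is the missing link if Part 1c leads to another dose.

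A reader might infer three stronger conclusions, which the documents do not support:

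- **Misattributed dose-limiting toxicities.** Section 10.2.2.1 describes the escalation parts as completed, with 100 mg BID declared as the RP2D alone and in combination. Movement between levels inside the DLT window is not a live risk.
- **A protocol-mandated overdose.** Section 16.5 defines overdose as "A dose that is higher than the dose that patient has been intended to receive", but it counts a modified dose as an intended one. A dose set under Table 12.1-1 can be read as that modified dose, so the conflict is only arguable.
- **A three-fold rise in exposure.** Comparing 50 mg at CrCl 100 with 100 mg at CrCl 60 gives 22,855 / 7,457 = 3.06. Of this, 11,428 / 7,457 = 1.53 comes from the fall in CrCl, and the dose change contributes 2.00. The result, 22,855, is also below the 26,826 projected for 100 mg at CrCl 50.

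**Conclusion.** The contradiction is real. On its wording, footnote 1 can list a dose above the one a patient was assigned, or above the one the same table set after toxicity. The clearest case is a restart at 50 mg BID for a patient previously reduced to 25 mg BID (2-fold). For patients on 50 or 75 mg BID with CrCl above 50, the listed 100 mg BID is 2 or 1.33 times the current dose. The 4-fold entry in the working is the extreme of the same literal reading, and a clinician would be most likely to question it.

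This rests on two assumptions: that a site applies the footnote as written, and that patients on less than 100 mg BID remain on treatment. The documents do not say how many there are, so the number affected cannot be estimated. The concern is that an individual patient's reduction is overridden. It is not that exposure leaves the range projected for the RP2D. The gap at CrCl 50 and the missing link to Part 1c are smaller defects in the same footnote.

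**What to change.** The sponsor's clinical team should reconcile footnote 1 with three things: the dose levels assigned in Parts 1a and 1b, the reductions in the other rows of Table 12.1-1, and the dose determination in Part 1c. The revised text should say which patients each line covers and how it relates to the dose already in force, including at restart after a hold. The CrCl bands should be made contiguous and consistent with Table 7.1-1. Which doses and rules apply is for the clinical team, and none is proposed here.

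The cost is footnote wording in the next amendment, or a clarification memo to sites. It needs no new data, patients or analyses.

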### 12.1.3.3 Supportive Care Guidelines

Patients should receive appropriate supportive care measures as deemed necessary by the treating Investigator. Guidelines outlined below should be used in conjunction with information provided in the pembrolizumab product label:

**Hyperammonemia:** Patients should be monitored for elevated venous plasma ammonia. Asymptomatic clinically significant drug-related elevations in ammonia (e.g., a repeatable elevation in ammonia > 2x ULN AND > 2x baseline) should be managed by interrupting INCB001158 study drug and monitoring to resolution. For symptomatic elevations (i.e., significant ammonia elevation associated with nausea, vomiting, severe anorexia, mental status changes, seizure, or other symptoms associated with hyperammonemia), patients should be admitted for management according to the local institutional protocol for hyperammonemia, including 1) sending appropriate labs [ammonia (on ice, measured STAT), plasma amino acid profile, LFTs, electrolytes, bicarb, BUN, creatinine, glucose, and urine orotic acid], 2) IV hydration with dextrose-containing fluids, 3) discontinuation of protein intake, 4) implementing therapy to reduce ammonia levels (oral lactulose/lacitol, IV Ammonul), and 5) identifying and treating any potential triggers (e.g., discontinue corticosteroids, treat infections, etc).

**Diarrhea:** Patients should be monitored for signs and symptoms of enterocolitis (such as diarrhea, abdominal pain, blood or mucus in stool, with or without fever) and of bowel perforation (such as peritoneal signs and ileus). In symptomatic patients, infectious etiologies should be ruled out, and if symptoms are persistent and/or severe, endoscopic evaluation should be considered. In patients with severe enterocolitis, treatment with systemic corticosteroids should be initiated at a dose of 1 to 2 mg/kg/day of prednisone or equivalent. In patients that do not respond to high dose steroids with 72 hr, consider initiation of additional immunosuppressive therapy (e.g., infliximab). When symptoms improve to Grade 1 or less, corticosteroid taper should be started and continued over at least 1 month.

In addition, patients with severe enterocolitis that are receiving INCB001158 monotherapy will have INCB001158 permanently discontinued, whereas, for patients receiving INCB001158/pembrolizumab combination, pembrolizumab will be permanently discontinued and INCB001158 will be withheld. Restarting INCB001158 may be considered in INCB001158/pembrolizumab combination patients if enterocolitis is not a toxicity associated with monotherapy INCB001158.

In patients with moderate enterocolitis, pembrolizumab should be withheld and antidiarrheal treatment should be started. If symptoms are persistent for more than one week, systemic corticosteroids should be initiated (e.g., 0.5 mg/kg/day of prednisone or equivalent). When symptoms improve to Grade 1 or less, corticosteroid taper should be started and continued over at least 1 month. Regarding guidelines for continuing treatment with INCB001158 and pembrolizumab, see [Table 12.1-2](#).

All patients who experience diarrhea should be advised to drink liberal quantities of clear fluids. If sufficient oral fluid intake is not feasible, fluid and electrolytes should be substituted via IV infusion.

**Nausea/vomiting:** Nausea and vomiting should be treated aggressively, and consideration should be given in subsequent cycles to the administration of prophylactic antiemetic therapy according to standard institutional practice. Patients should be strongly encouraged to maintain liberal oral fluid intake. Since nausea/vomiting can be a symptom of hyperammonemia, there should be a low threshold to test plasma ammonia levels for patients with nausea, vomiting, or new onset anorexia.

**Anemia:** Transfusions and/or erythropoietin may be utilized as clinically indicated for the treatment of anemia, but should be clearly noted as concurrent medications.

**Neutropenia:** Prophylactic use of colony-stimulating factors including Granulocyte Colony-Stimulating Factor (G-CSF), pegylated G-CSF or Granulocyte Macrophage Colony-Stimulating Factor (GM-CSF) is not allowed in this study. Therapeutic use of G-CSF is allowed in patients with Grade 3-4 febrile neutropenia.

**Thrombocytopenia:** Transfusion of platelets may be used if clinically indicated. Idiopathic thrombocytopenic purpura (ITP) should be ruled out before initiation of platelet transfusion.

**Anti-infectives:** Patients with a documented infectious complication should receive oral or IV antibiotics or other anti-infective agents as considered appropriate by the treating Investigator for a given infectious condition, according to standard institutional practice.

**Immune-related adverse events:** Patients who develop a Grade 2 or higher irAE (e.g., colitis, skin rash, hepatitis, uveitis, hypo- or hyperthyroidism, hypophysitis, or any other), should be discussed immediately with the Medical Monitor. Depending on the type and severity of an irAE, oral or IV treatment with a corticosteroid should be considered, in addition to appropriate symptomatic treatment of a given condition. For severe immune-mediated adverse events that do not respond to high dose IV steroids within 72 hours, consider initiation of additional immunosuppressive therapy (e.g., infliximab for non-hepatic toxicities or mycophenolate mofetil for immune-mediated hepatotoxicity).

**Dose modification and toxicity management of infusion reactions related to pembrolizumab:** Pembrolizumab may cause severe or life-threatening infusion reactions, including severe hypersensitivity or anaphylaxis. Signs and symptoms usually develop during or shortly after drug infusion and generally resolve completely within 24 hours of completion of infusion. Dose modification and toxicity management guidelines for pembrolizumab-associated infusion reactions are provided in [Table 12.1-3](#).

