Pneumonitis	Grade 2	Withhold	
 
Administer corticosteroids (initial dose of 1 - 2 mg/kg prednisone or equivalent) followed by taper
 
Add prophylactic antibiotics for opportunistic infections
 
	
 
Monitor participants for signs and symptoms of pneumonitis
 
Evaluate participants with suspected pneumonitis with radiographic imaging and initiate corticosteroid treatment
 

	Recurrent Grade 2, Grade 3 or 4	Permanently discontinue		
Diarrhea / Colitis	Grade 2 or 3	Withhold	
 
Administer corticosteroids (initial dose of 1 - 2 mg/kg prednisone or equivalent) followed by taper
 
	
 
Monitor participants for signs and symptoms of enterocolitis (ie, diarrhea, abdominal pain, blood or mucus in stool with or without fever) and of bowel perforation (ie, peritoneal signs and ileus)
 
Participants with <math>\geq</math>Grade 2 diarrhea suspecting colitis should consider GI consultation and performing endoscopy to rule out colitis
 
Participants with diarrhea/colitis should be advised to drink liberal quantities of clear fluids. If sufficient oral fluid intake is not feasible, fluid and electrolytes should be substituted via IV infusion
 

	Recurrent Grade 3 or Grade 4	Permanently discontinue		

**Table 12.1-2: Dose Modification and Toxicity Management Guidelines for Immune-Related Adverse Events Associated With Pembrolizumab (Parts 1b, 1c, and 3) (Continued)**

irAEs	Toxicity Grade (CTCAE V4.0)	Action With Pembrolizumab	Corticosteroid and/or Other Therapies	Monitoring and Follow-up
AST or ALT elevation or Increased Bilirubin	Grade 2 a	Withhold	
 
Administer corticosteroids (initial dose of 0.5 - 1 mg/kg prednisone or equivalent) followed by taper
 
	
 
Monitor with liver function tests (consider weekly or more frequently until liver enzyme value returned to baseline or is stable)
 

	Grade 3 b or 4 c	Permanently discontinue	
 
Administer corticosteroids (initial dose of 1 - 2 mg/kg prednisone or equivalent) followed by taper
 
	

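### For severe enterocolitis, Protocol Section 12.1.3.3 and Tables 12.1-1 and 12.1-2 give incompatible instructions on stopping or withholding treatment, and no precedence is stated

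*Protocol*

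**What the plan says.** **Section 12.1.3.3 (Diarrhea).** For severe enterocolitis in combination patients, "pembrolizumab will be permanently discontinued and INCB001158 will be withheld". The section adds: "Restarting INCB001158 may be considered in INCB001158/pembrolizumab combination patients if enterocolitis is not a toxicity associated with monotherapy INCB001158". For monotherapy it says that "patients with severe enterocolitis that are receiving INCB001158 monotherapy will have INCB001158 permanently discontinued". For moderate enterocolitis lasting more than one week, "systemic corticosteroids should be initiated (e.g., 0.5 mg/kg/day of prednisone or equivalent"). It then sends the reader to Table 12.1-2 for continuing both drugs.

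**Table 12.1-2 (pembrolizumab; Parts 1b, 1c and 3).** The row reads "Diarrhea / Colitis Grade 2 or 3 Withhold". Permanent discontinuation is reserved for "Recurrent Grade 3 or Grade 4". Among the general instructions: "If pembrolizumab has been withheld, pembrolizumab may resume after the irAE decreased to" Grade 1 or lower, after the corticosteroid taper.

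**Table 12.1-1 (INCB001158; all parts).** Colitis is listed under suspected immune-related events. At Grade 3 the drug is interrupted. After a first event the instruction is "Consider restarting at next lower dose level upon resolution to" Grade 1 or lower; after a second event the drug is stopped permanently. At Grade 4 it is stopped permanently.

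**What severe means.** Section 12.1.2 pairs severe with Grade 3/4 when it describes management of immune-related toxicity, and the fallback severity scale in Section 16.1.2 describes Grade 3 as severe.

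**The concern.** Colitis is among the immune-related toxicities that the protocol expects, and the question here is whether a patient may be given a drug again after a severe episode. In some situations one text permits a restart that the other rules out. A site or Medical Monitor looking for the rule finds two and cannot tell which one applies.

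There is also a reporting consequence. SAP Section 8.2.3 counts adverse events and immune-related events leading to interruption, dose reduction and permanent discontinuation, with separate rows for each drug. If two policies are in force, the same clinical event can fall in different rows depending on which text was followed.

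**Working it through.** No arithmetic on trial data applies. The check sets the texts side by side for each drug and regimen (pembrolizumab in combination, INCB001158 monotherapy, INCB001158 in combination) and each severe event (first Grade 3, second or recurrent Grade 3, Grade 4): 3 × 3 = 9 combinations.

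| Drug and regimen | Event | Section 12.1.3.3 | Table | Result |
|---|---|---|---|---|
| Pembrolizumab, combination | First Grade 3 | Stop permanently | 12.1-2: withhold, may resume | Conflict (1) |
| Pembrolizumab, combination | Recurrent Grade 3 | Stop permanently | 12.1-2: stop permanently | Agree |
| Pembrolizumab, combination | Grade 4 | Stop permanently | 12.1-2: stop permanently | Agree |
| INCB001158, monotherapy | First Grade 3 | Stop permanently | 12.1-1: interrupt, consider restart at next lower level | Conflict (2) |
| INCB001158, monotherapy | Second Grade 3 | Stop permanently | 12.1-1: stop permanently | Agree |
| INCB001158, monotherapy | Grade 4 | Stop permanently | 12.1-1: stop permanently | Agree |
| INCB001158, combination | First Grade 3 | Withhold, conditional restart | 12.1-1: interrupt, consider restart at next lower level | Broadly compatible |
| INCB001158, combination | Second Grade 3 | Withhold, conditional restart | 12.1-1: stop permanently | Differ, but largely settled by 12.1.3.2 |
| INCB001158, combination | Grade 4 | Withhold, conditional restart | 12.1-1: stop permanently | Conflict (3) |

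The second Grade 3 event in combination is not counted as a conflict. Section 12.1.3.2 already requires INCB001158 to be stopped for a recurrence at Grade 3 or above when it was restarted after permanent discontinuation of pembrolizumab. That leaves three conflicts in nine.

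**Can the meaning of severe remove them?** If severe meant Grade 4 only, conflicts 1 and 2 would go but 3 would stay. If it meant Grade 3 only, 3 would go but 1 and 2 would stay. Under the protocol's own Grade 3/4 usage, all three stand.

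**Direction.** In conflicts 1 and 2 the section is the stricter text. In conflict 3 the table is. The mismatch is therefore not one source being uniformly more cautious than the other.

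**Moderate (Grade 2) colitis, corticosteroids.**

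| Source | When to start | Starting dose (prednisone or equivalent) |
|---|---|---|
| Section 12.1.3.3 | After more than one week | 0.5 mg/kg/day, as an example |
| Table 12.1-1 | After more than 5 days | 0.5 to 1 mg/kg/day |
| Table 12.1-2 | No waiting period stated | 1 to 2 mg/kg |

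The trigger differs in all three places. The section's dose differs from Table 12.1-2 but overlaps Table 12.1-1.

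**Cross-reference.** Section 12.1.3.3 points to Table 12.1-2 for continuing INCB001158, yet that table's action column covers pembrolizumab only.

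**The case against.** Several points count against a strong reading, and most of them stand in part.

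- *These are guidelines.* Section 12.1.3.1 says that the parameters do not override clinical judgment and asks for Medical Monitor contact when a dose modification is planned. Section 12.1.3.3 requires immediate discussion of any immune-related event of Grade 2 or higher. This central step should reduce divergence. It does not remove the conflict, because the Medical Monitor works from the same texts.
- *The tables govern.* Section 12.1.3.1 sends combination immune-related events to both tables. It does not say that they displace Section 12.1.3.3, whose wording for severe enterocolitis is mandatory, and that sentence does not cover monotherapy.
- *The texts are not opposites.* This is correct. A reader might infer that they require opposite actions on both drugs at every severe event. In each conflict one text permits a restart that the other excludes, and neither requires a restart. For INCB001158 in combination, a first Grade 3 event is an interruption under both texts.
- *Different treatment by site is not shown.* This is also correct. The documents show that the same event can be handled differently, not that it was.
- *Primary endpoints are untouched.* A reader might infer that a primary endpoint is corrupted. The named primary endpoints are adverse events and changes in laboratory values, vital signs and physical examinations. Interruption and discontinuation counts are SAP summary rows.
- *Few events are likely.* Table 10.1-2 lists diarrhoea in 2 of 23 patients, none at Grade 3 or higher, and Section 10.2.2.1 reports no Grade 3 treatment-related event at 100 mg BID in combination. These early data suggest small numbers, but they do not settle what a site should do when an event occurs.

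**Conclusion.** The point holds as an internal inconsistency in the protocol. Three of nine drug, regimen and event combinations carry incompatible instructions: pembrolizumab at a first Grade 3 event, INCB001158 monotherapy at a first Grade 3 event, and INCB001158 in combination at Grade 4. The differing corticosteroid triggers for moderate colitis and the misdirected cross-reference add to it.

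For the SAP summaries, a first Grade 3 event can be counted as a discontinuation or as an interruption or reduction for INCB001158 in monotherapy, and as a discontinuation or an interruption for pembrolizumab in combination. A Grade 4 event can be counted either way for INCB001158 in combination.

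The conclusion rests on reading severe as Grade 3/4, which is the protocol's own usage; at least one conflict survives if it is read as either grade alone. The number of patients affected cannot be estimated, because the documents give no expected rate of severe colitis.

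**What to change.** The sponsor should reconcile Section 12.1.3.3 with Tables 12.1-1 and 12.1-2 so that each drug, regimen, CTCAE grade and event number has one consistent instruction. The corticosteroid trigger and starting dose for moderate colitis should be reconciled in the same pass, and the Section 12.1.3.3 cross-reference for INCB001158 corrected. Which rule is right is for the sponsor and its clinical advisers, and no view is given here.

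The cost is protocol wording. No change to the design, the sample size or the SAP's planned tables is needed.
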